8.3 Assignment to Treatment Groups

All eligible subjects will be randomized to receive tipifarnib administered according to one of the following dose regimens:

- Regimen 1: 600 mg bid for 7 days on Days 1-7 in 28 day cycles (i.e. 1 week on / 3 weeks off).
- Regimen 2: 300 mg bid for 21 days on Days 1-21 in 28 day cycles (i.e. 3 weeks on / 1 week off).

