Upon review of the first 9 subjects enrolled in the study, the investigators noted that the alternative week regimen may not provide sufficient recovery time in subjects who experience myelosuppressive effects of tipifarnib. Therefore, the protocol was amended (Amendment 2) to adjust the treatment administration schedule to bid on Days 1-7 of 28 day treatment cycles. The investigators considered that by adjusting the dose regimen to allow for a 3 week rest period following each week of dosing, the myelosuppressive effects will be mitigated allowing subjects to make gains on increasing the cell counts as the cycles progress. Additionally, given the prior experience and tolerability with 300 mg bid on Days 1-21 of 28 day treatment cycles, this regimen was incorporated into Amendment 2 to support dose selection in future clinical studies.

[figure not shown]
Both dose regimens are expected to be well tolerated and to potentially provide clinical benefit to subjects with MDS. Furthermore, the current study allows for step-wise 100 - 200 mg dose adjustment based on subject tolerability. The data obtained from this study will be used to select the optimal dose and dose regimen to support the further development of tipifarnib in subjects with MDS

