10.4 Abnormal Laboratory Findings and Other Abnormal Investigational Findings

Abnormal laboratory findings and other abnormal investigational findings (e.g. on an ECG trace) should not be reported as AEs unless they are associated with clinical signs and symptoms, lead to treatment discontinuation or are considered otherwise medically important by the Investigator. If an abnormality fulfills these criteria, the identified medical condition, e.g. anemia, increased alanine aminotransferase (ALT), must be reported as the AE rather than the abnormal value itself.

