11.3 Day 1 (± 2 days) of Cycle 2 and every cycle thereafter

The following assessments will be conducted:

- Record any RBC, whole blood and platelet transfusions that were received since the last study visit.
- Record concomitant medications
- Assessment of AEs
- Assess ECOG performance status.
- Symptom based physical examination
- Perform urine or serum pregnancy test for females of child-bearing potential only
- Perform serum chemistry laboratory tests (AST, ALT, total bilirubin, creatinine, BUN, potassium and calcium). Subjects are not required to be fasting. If clinically indicated, serum chemistry tests may be repeated more frequently.
- Perform hematology tests: hemoglobin, reticulocytes, platelets, WBCs, neutrophils, neutrophil precursors (promyelocytes, myelocytes, metamyelocytes, band neutrophils), monocytes, lymphocytes and blasts. If clinically indicated, hematology tests may be repeated more frequently.

• Conduct a drug accountability on the returned empty bottles and unused medications.

11.4 Day 22 (\pm 5 days) of Cycles 3 and every approximately 12 weeks thereafter (e.g. 6, 9, 12, etc.)

The timing of the hematologic and disease assessments should be maintained as much as possible independently of potential treatment cycle delays.

The following procedures will be performed during the Day 22 visit:

- Record any RBC, whole blood and platelet transfusions that were received since the last study visit.
- Record concomitant medications

- Assessment of AEs
- Symptom based physical examination
- Perform hematology tests: hemoglobin, reticulocytes, platelets, WBCs, neutrophils, neutrophil precursors (promyelocytes, myelocytes, metamyelocytes, band neutrophils), monocytes, lymphocytes and blasts
- Perform disease and response assessment:
 - O Perform bone marrow aspirate for disease assessment, cytogenetic assessment and NGS oncogene panel during Cycles 3, 6 and 9 only. Thereafter, bone marrow evaluations will occur as per institutional standard practice. If the bone marrow aspirate is inadequate, a bone marrow biopsy should be performed. If on this bone marrow sample, a CR or PR is observed, a bone marrow aspirate with cytogenetic assessment must be repeated 1 month later, i.e. prior to the end of the next cycle.
 - o Investigator review of subject RBC transfusions, hematology and bone marrow evaluation (if available) for completion of response assessment.

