10.2. Clinical Laboratory Evaluations

Hematological toxicities Grade 3 or above based on NCI-CTCAE version 4.03 criteria will be summarized across all treatment cycles. A shift table will be presented for the shift from baseline to worst post-baseline severity grade. Severity grading is based on the National Cancer Institute Common Terminology Criteria for Adverse Events (CTCAE), version 4.03, with normal ranges defined from the American Medical Association Standard Lab Normal Ranges. For laboratory values that fall outside the defined severity ranges, a value of 0 was entered. Not Applicable is given to those laboratory values that have no associated CTCAE severity criteria.

The data for clinical laboratory evaluations (including hematology, chemistry, coagulation, and pregnancy testing) will be presented in listings. In addition to the results, these listings will present the normal range, toxicity grade, and clinical assessment (Normal; Abnormal, but not clinically significant; Abnormal, clinically significant) associated with evaluations.

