13. DATA HANDLING CONVENTIONS

Analyses will be performed using SAS® [SAS Institute 2011] Version 9.3 or higher.

The clinical database will be locked prior to the initiation of the Stage 1 statistical analyses. A database lock is defined as a stable database that can be analyzed and reported. Changes to a locked database must be authorized in writing by the study sponsor [REDACTED]

The data conventions include the following.

- Data will be described and summarized by study stage (Stage 1 or Stage 2), Stage 1 cohort (starting dose level and schedule), or Stage 2 cohort (disease type).
- Summary tables for continuous variables will contain the following statistics: N (number of subjects in the population); n (number of subjects with data for that variable); mean; standard deviation; median; minimum; and maximum. Selected statistics may also include 2 sided 95% normal approximation confidence intervals (CI) on the mean.
- Summary tables for categorical variables will include: N (number of subjects in the denominator); n (number of subjects in the numerator); and percent. Selected statistics also may include 2-sided 95% CIs for the percent, calculated using the CL=AGRESTICOULL option in SAS PROC FREQ.

- The baseline value for a given parameter is the last value prior to the first dose. A value is considered to be post-baseline if it is obtained after the first dose. A value is considered to be postdose on a given cycle day if it is obtained after the dose is administered on that day.
- Data from all study centers will be pooled for all analyses.
- Unless otherwise specified, statistical testing will be 2-sided at a nominal 0.05 level of significance.
- Study day is defined as calendar date – date of first treatment + 1 if the calendar date is on or after the date of first treatment, and calendar date – date of first treatment if the calendar date is before the date of first treatment
- Measurements from unscheduled visits will be included in listings, but not summary tables.
- Missing data conventions for individual endpoints are described in the SAP section for the endpoint.
- Additional exploratory analyses may be performed as deemed appropriate after review of the pre-specified analyses. Log-transformations or nonparametric tests may be applied to measurements displaying a significant degree of non-normality.
- Listings will be provided for all data collected in the eCRF.

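### SAP 13 keeps all unscheduled measurements out of summary tables, so the worst-grade and grade 3 or above laboratory tables may omit low counts that were measured

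*SAP*

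**What the plan says.** - **SAP 13** sets a general rule without exceptions: "Measurements from unscheduled visits will be included in listings, but not summary tables". The same section treats any value obtained after the first dose as post-baseline.
- **SAP 10.2** plans a summary of hematological toxicities of grade 3 or above over all cycles, and also: "A shift table will be presented for the shift from baseline to worst post-baseline severity grade". It does not mention scheduled or unscheduled draws.
- **Protocol 11.3** places routine hematology at "Day 1 (± 2 days) of Cycle 2 and every cycle thereafter" and adds: "If clinically indicated, hematology tests may be repeated more frequently". Under Table 1 and protocol 11.4, a second count is scheduled on Day 22 (±5 days), but only in Cycles 3, 6, 9, 12 and every third cycle after that.
- **Protocol 8.3** gives the dosing days: "Regimen 1: 600 mg bid for 7 days on Days 1-7 in 28 day cycles" and "Regimen 2: 300 mg bid for 21 days on Days 1-21 in 28 day cycles".
- **Protocol 10.4** says that abnormal laboratory findings "should not be reported as AEs unless they are associated with clinical signs and symptoms", lead to treatment discontinuation, or are otherwise considered medically important by the investigator. Protocol 9.11 requires an AE entry when therapy is given for a new or worsening condition.
- **Protocol 12.2.2** plans grade 3 and 4 hematological toxicity without excluding unscheduled values, and includes unscheduled as well as scheduled time points for vital signs. SAP 10.4 keeps only the scheduled ones. SAP 15 lists no changes from the protocol.

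**The concern.** A worst post-baseline grade should be taken over every value observed after the first dose. By SAP 13's own definition an unscheduled count after the first dose is post-baseline, yet the next rule bars it from any summary table. A programmer who follows the SAP literally leaves it out of the two tables meant to show the depth of myelosuppression.

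The excluded values are not a random subset. Extra counts are drawn when clinically indicated, and scheduled counts in most cycles come after the rest period.

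Safety and tolerability belong to the first secondary objective. Amendment 2 changed the schedule because of myelosuppression, on the view that with a longer rest "the myelosuppressive effects will be mitigated allowing subjects to make gains on increasing the cell counts as the cycles progress". Protocol 9.4 says the data will be used to choose the dose and regimen. Tables that leave out measured lows would bear directly on that choice.

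**Working it through.** The documents state no figure for this point, so there is nothing to reproduce. The check is calendar arithmetic, followed by an illustration under stated assumptions.

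**Inputs.** The last dosing day is Day 7 (Regimen 1) or Day 21 (Regimen 2), from protocol 8.3. The next cycle's Day 1 is Day 29 on the current cycle's count, ±2 days. The other scheduled count is Day 22 ±5 days, every third cycle.

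**Step 1. Days from last dose to scheduled count** (visit day minus last dosing day):

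| Count | Regimen 1 | Regimen 2 |
|---|---|---|
| Day 1 of next cycle | 29 − 7 = 22 (20 to 24) | 29 − 21 = 8 (6 to 10) |
| Day 22, every third cycle | 22 − 7 = 15 (10 to 20) | 22 − 21 = 1 (4 days before the last dose to 6 days after) |

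**Step 2. How often each count occurs.** Three cycles give three next-cycle Day 1 counts and one Day 22 count. Day 22 supplies 1/(3 + 1) = 25% of scheduled post-dose counts. Two of every three cycles, including Cycles 1 and 2, have only the next Day 1 count. For a subject who stops treatment, the End of Treatment count replaces it, at about 30 ± 7 days after the last dose unless other anticancer treatment starts sooner.

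**Step 3. Illustration.** The documents give no nadir time. Assume a nadir a fixed number of days after the last dose, and call it seen if a scheduled count on its nominal date falls within 5 days of it. Cycles seen, out of the first three:

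| Assumed nadir, days after last dose | Regimen 1 | Regimen 2 |
|---|---|---|
| 0 | 0 of 3 | 1 of 3 |
| 3 | 0 of 3 | 3 of 3 |
| 7 | 0 of 3 | 3 of 3 |
| 10 | 1 of 3 | 3 of 3 |
| 14 | 1 of 3 | 0 of 3 |

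For assumed nadirs from 0 to 10 days, scheduled counts see fewer Regimen 1 lows. At 14 days the order reverses. With a 7-day tolerance the 14-day row becomes 1 of 3 and 3 of 3. The direction therefore depends on the assumption, and these are not estimates for this trial.

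**Step 4. What other tables recover.** SAP 10.1 tabulates hematology-related TEAEs, including by maximum toxicity grade, whatever the visit type. A low count reaches those tables if it was symptomatic, led to discontinuation, was judged medically important (protocol 10.4), or was a new or worsening condition that was treated (protocol 9.11). SAP 10.3 summarises transfusion and growth factor support. What remains is a measured, untreated, asymptomatic low not judged important. That value appears only in listings.

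**The case against.** The strongest reply is that little is lost. Lows that were acted on with treatment should be reported as AEs under protocol 9.11, and every value stays in the listings. This is largely right and narrows the point to the laboratory-based tables. It does not rescue them: a table labelled worst post-baseline grade should not depend on whether the visit was planned.

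Four stronger readings are tempting, and the documents do not support them.

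- **That scheduled counts always fall at recovery and so miss the nadir.** Day 22 counts do not fit that description. In Regimen 2 they come about 1 day after the last dose, and even the Day 1 count, 6 to 10 days after it, may lie near the nadir. Without a nadir time, only the word may is justified.
- **That SAP 13 itself biases the regimen comparison.** The 22-versus-8-day difference comes from the dosing and visit schedules. SAP 13 removes a partial remedy. Restoring the extra counts would not equalise ascertainment, because they are clinically driven in an open-label study, and a low that nobody sampled stays unseen.
- **That a particular share of subjects would drop out of the table.** No document gives a rate. Subjects must enter with neutrophils below 1000/mm³, so some may show their worst grade at a scheduled visit anyway.
- **That AE tables do not help at all.** Step 4 of the working shows that they capture part of the loss.

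One limit also stands. Section 9.5 of the protocol, some rows of the schedule and the table shells are not in the public text. They might require further counts or define the tables differently.

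**Conclusion.** The point holds in limited form. As written, SAP 13 conflicts with its own definition of post-baseline and with the purpose of the SAP 10.2 tables. The worst-grade shift table and the grade 3 or above summary may leave out measured low counts and so understate laboratory toxicity. The loss may be greater in Regimen 1, where the usual scheduled count comes 20 to 24 days after the last dose against 6 to 10 days in Regimen 2. That direction is an inference from timing and depends on when the nadir falls. Its size cannot be computed from the documents.

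Separately, and without any assumption, SAP 10.4 narrows the vital-sign summaries that protocol 12.2.2 plans, and SAP 15 does not record it.

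This should be fixed before the laboratory tables are produced. It does not touch the primary response rate, the stage 1 rule or the 4-of-18 decision.

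**What to change.** 1. In SAP 13, limit the exclusion of unscheduled measurements to by-visit descriptive summaries.
2. In SAP 10.2, state that the worst-grade, shift and grade 3 or above tables use every post-baseline laboratory value, scheduled or unscheduled, and are shown by regimen.
3. In SAP 10.4, restore unscheduled vital signs as protocol 12.2.2 plans, or record the change and its reason in SAP 15. If they are restored, SAP 13 must allow it.
4. Bring the table shells into line. It would help to report the number of counts per subject-cycle by regimen, so that readers can judge how evenly the regimens were sampled.

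The cost is a few sentences and some reprogramming. No new data are needed, because the values are already to be listed. Reported toxicity rates may be higher than under the present rule. Because unscheduled draws are clinically driven in an open-label study, ascertainment may still differ between regimens, and the report should say so.

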14. REPORTING CONVENTIONS

The table, listing and figure reporting layout will be detailed in the companion document *KO-TIP-003 Safety Table, Listing and Figure Shells*.

15. CHANGES IN THE STATISTICAL METHODS FROM THOSE STATED IN THE PROTOCOL

None.

17. TABLES, FIGURES, LISTINGS

Tables, listings and, if applicable, figures will be generated according to the companion document which details the layout of the output. Minor style deviation from specification defined in the shell document in the final production is permissible.
